## 10.1 MRI Parameters

Data for MRI parameters detailed in [Section 2.3.2](#) will be delivered in a raw file provided by the MRI Core Lab. Observed values, absolute changes from baseline, and percent changes from baseline will be listed and summarized. Summary tables will include p-values for treatment group comparisons of changes from baseline.

Regional wall motion will be analyzed using average (over slices) end diastolic wall thickness, end systolic wall thickness, and wall thickening. Sixteen-segment data correspond to coronary region as follows:

- Left anterior descending artery = segments 1, 2, 7, 8, 13, and 14.
- Left circumflex artery = segments 5, 6, 11, 12, and 16.
- Right coronary artery = 3, 4, 9, 10, and 15.

Different coronary anatomy will be associated with specific segments on a case-by-case basis. Analysis parameters will be observations averaged over the infused segments. For example, if the infused segment is via the right coronary artery, wall thickening for that location will be the mean “average” wall thickening over segments 3, 4, 9, 10, and 15.

Regional wall motion will also be analyzed according to circumferential location as follows:

- Anterior = 1, 7, and 13
- Lateral = 5, 6, 11, 12 and 16
- Inferior = 4, 10, and 15
- Septal = 2, 3, 8, 9, and 14

Of note, segments 2 and 3 will be excluded for all wall thickness analyses.

Scar size, non-viable tissue, and circumferential strain will be analyzed both overall as well as by individual segments and the following groups of segments:

- By coronary artery territory as follows:
  - Left anterior descending artery = segments 1, 2, 7, 8, 13, and 14
  - Left circumflex artery = segments 5, 6, 11, 12, and 16
  - Right coronary artery = 3, 4, 9, 10, and 15
- By circumferential location as follows:
  - Anterior = 1, 7, and 13
  - Lateral = 5, 6, 11, 12 and 16
  - Inferior = 4, 10, and 15
  - Septal = 2, 3, 8, 9, and 14

Listings of MRI parameters will include observed values, changes from baseline, and percent changes from baseline. A summary table will include p-values for treatment group comparisons of changes from baseline.

MRI overreaders will be blinded to treatment assignment but not to temporal order of the images; e.g., readers will have access to and will use baseline and Month 6 images when reading Month 12 images (informed reading).

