**Study Design:**

Male subjects at least 12 years of age, with cardiomyopathy secondary to DMD, and meeting all inclusion and no exclusion criteria, will be randomized. Each subject that meets all eligibility criteria will be randomized in a 1:1 manner to either investigational product (CAP-1002) or usual care.

If randomized to investigational product, a subject will receive an intracoronary infusion of CAP-1002 (intended total dose of 75 million [75M] cells) in three coronary arteries supplying the three major cardiac territories of the left ventricle of the heart (anterior, lateral, inferior/posterior). All three major cardiac territories will be treated (infused) during a single procedure in an open-label fashion.

Subjects randomized to receive usual care will not receive an infusion. They will continue to be cared for and treated in whatever manner the investigator deems most appropriate for the subject on an ongoing basis, except that usual care cannot include treatment with CAP-1002 or other investigational treatments.

Approximately 24, and not more than 30, subjects will be randomized into the study in two sequential enrollment groups. Safety data from Group 1 will undergo a Data Safety Monitoring Board (DSMB) review prior to initiation of enrollment for Group 2.

The first 6-8 randomized subjects will comprise Group 1, and will include a minimum of 3 subjects completing intracoronary infusion with CAP-1002. The DSMB will conduct a review of interim safety data through 72 hours post -Day 0 for at least 3 infused subjects and for at least 6 subjects overall.

Enrollment of Group 2 will begin per DSMB recommendations following their review of the 72 hour safety data from Group 1. Group 2 will include approximately 18 subjects.

Screening and randomization will continue until at total of 12 subjects are infused with CAP-1002 or 30 subjects are randomized into the study, whichever comes first.

CCI

Subject infusions will be staggered by at least three days to allow for detection of acute procedure-related complications should they occur. Additionally, subject infusions in Group 2 will not begin until at least two weeks after the final infusion occurs in Group 1, to allow for completion of the Group 1 safety data review through 72 hours post Day 0.

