### **3.4 Rationale for Study Design and Control Group**

Male subjects with cardiomyopathy secondary to DMD are being recruited for this trial. DMD is an x-linked disease. Females only develop DMD when they are homozygous for the condition. This is so extremely rare that the chance of recruiting enough female subjects to this trial to make any safety conclusions makes the exclusion of females appropriate in this situation.

An open control group receiving usual care has been chosen for this study in order to have a clear comparator for safety efficacy. It was not felt reasonable to have control subjects undergo either multi-vessel placebo infusion or a sham procedure.

Cardiac involvement can start in childhood or adolescence and progress at a variable rate. While most adults with DMD have significant evidence of cardiac involvement, a significant proportion of adolescents have progressive significant cardiac involvement supporting the need to investigate the safety and effectiveness of this treatment in subjects at least 12 years of age.

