## 6.10 Infusion Procedure

### 6.10.1 CAP-1002 Infusion

Every attempt should be made to infuse the three major cardiac territories of the left ventricle (anterior territory, lateral territory, and inferior/posterior territory). Additionally, the infusing Investigator may alter the infusion plan during the infusion procedure when deemed clinically necessary. The procedure will be performed as follows:

CCI

A large block of text has been redacted with a black rectangular box. The redacted text begins with the acronym 'CCI' in red, followed by several lines of blacked-out text. The redacted area is approximately 10 lines high and 80 characters wide.

CCI

Following intracoronary infusion, subjects will be observed in the hospital for 20-24 hours with continuous cardiac (telemetry) monitoring. Troponin and CK-MB laboratory studies and vital signs (temperature, HR, BP, and RR) will be monitored every 8 hours ( $\pm 30$  minutes) from the end of the infusion. A total of three sets of cardiac enzymes will be evaluated to rule out cardiac injury during the post-infusion hospital stay through discharge. If the subject is discharged prior to 24 hours, cardiac enzymes will be drawn just prior to discharge.

Prior to discharge from the hospital, a physical assessment will be performed which will include chest pain assessment, review of laboratory results, 12-lead ECG, and arterial puncture site as well as assessment of adverse events. In the absence of serious adverse events, subjects will be discharged per standard of care practice.

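### The territory-level wall-motion parameter in SAP 10.1 is averaged over infused segments, which usual-care subjects do not have, and no counterpart rule is given for them

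*SAP*

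**What the plan says.** SAP 10.1 assigns the 16 left-ventricular segments to three arteries by default. It then adds two rules for regional wall motion. Where anatomy departs from the default, "Different coronary anatomy will be associated with specific segments on a case-by-case basis". For the quantity analysed, "Analysis parameters will be observations averaged over the infused segments". The one worked example takes the right coronary artery and averages wall thickening over its default segments.

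The same section says: "Summary tables will include p-values for treatment group comparisons of changes from baseline".

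In the control arm, the Protocol synopsis (Study Design) states: "Subjects randomized to receive usual care will not receive an infusion". Protocol 3.4 explains that there is no substitute procedure: "It was not felt reasonable to have control subjects undergo either multi-vessel placebo infusion or a sham procedure". Footnote 1 of Protocol Appendix 1 adds that usual-care subjects have no Day 0 visit.

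In the CAP-1002 arm, Protocol 6.10.1 aims at complete coverage: "Every attempt should be made to infuse the three major cardiac territories of the left ventricle". It also allows departures: "the infusing Investigator may alter the infusion plan during the infusion procedure when deemed clinically necessary".

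SAP 10.1 has a second regional analysis that does not refer to infusion: "Regional wall motion will also be analyzed according to circumferential location as follows", followed by fixed anterior, lateral, inferior and septal lists.

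**The concern.** A parameter compared between randomized arms should have the same definition in both. This one is defined by something that happens in one arm only. Read literally, it has no value for a usual-care subject. The natural repair is to give controls the default map. The CAP-1002 value would then depend on which territories were infused, which is a post-randomization event, and on anatomy that study angiography can show only in that arm. The p-value could then reflect a difference in the regions or subjects compared as well as any treatment effect.

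The SAP recognises this kind of problem elsewhere. Section 2.3.1 gives usual care a reference time point in place of infusion time. Section 9.1 gives each usual-care subject a randomly chosen matched donor for the donor-specific antibody analysis. Infused segments have no such counterpart.

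**Working it through.** The documents state no effect size, SD or power for regional wall motion, so there is no plan figure to reproduce. The check covers the segment lists, the two readings of the averaging rule, and an illustration under stated assumptions.

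**1. Segment lists (SAP 10.1).** Segments 2 and 3 are excluded from wall thickness analyses.

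| Territory | Default segments | Count | Count without 2 and 3 |
|---|---|---|---|
| LAD | 1, 2, 7, 8, 13, 14 | 6 | 5 |
| LCX | 5, 6, 11, 12, 16 | 5 | 5 |
| RCA | 3, 4, 9, 10, 15 | 5 | 4 |
| Total | | 16 | 14 |

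Each segment appears once (6 + 5 + 5 = 16). The circumferential lists also cover each segment once (3 + 5 + 3 + 5 = 16). Either map can therefore be applied to any subject, infused or not.

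**2. When the arms agree.** If all three territories are infused and anatomy is standard, the infused set is the full default map (14 segments after exclusion). Controls on the default map then have the same segments.

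**3. When they do not.** Incomplete infusion does not remove a subject from the analysis. SAP 6 requires receipt of the product and one post-baseline value, and SAP 8.6 plans to tabulate the combination of territories infused and reasons for non-completion. The rule can be read in two ways:

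- *Pooled over infused segments.* A missed RCA removes 4/14 = 28.6%. A missed LAD or LCX removes 5/14 = 35.7%. A control loses none.
- *Each territory separately, as the worked example suggests.* The subject has no value for the missed territory. If 1 of 12 CAP-1002 subjects is affected, that comparison has 12 - 1 = 11 against all 12 controls. The segments match under standard anatomy, but the CAP-1002 subjects are selected by procedural outcome.

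Remapped anatomy changes the segment set under either reading.

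**4. Illustration of size (assumed inputs).** Let a share f of 12 CAP-1002 subjects have a different segment set, and let that set shift the mean change by g SD. With 12 per arm (SAP 4) and two-sided 0.05 (SAP 7.3), by normal approximation:

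- between-arm shift b = f × g;
- standard error = sqrt(2/12) = 0.408 SD;
- type I error = P(|Z + b/0.408| > 1.96).

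| f | g | b (SD) | Type I error |
|---|---|---|---|
| 1/12 | 0.25 | 0.021 | 0.050 |
| 2/12 | 0.5 | 0.083 | 0.055 |
| 4/12 | 0.5 | 0.167 | 0.069 |
| 4/12 | 1.0 | 0.333 | 0.129 |

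For scale, 80% power at this size needs about (1.96 + 0.84) × 0.408 = 1.14 SD. With one fixed list in both arms, b from this source is 0 and the error stays at 0.05.

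**5. An inconsistency in the same section.** The RCA wall-thickening example averages segments 3, 4, 9, 10 and 15, although segment 3 is among those excluded from wall thickness analyses. The 14-segment counts above take the exclusion to cover wall thickening.

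**The case against.** The strongest reply is that little is exposed. All three territories are meant to be infused, and with standard anatomy the infused set then equals the default map. The circumferential wall-motion analysis is like with like already. Scar size, non-viable tissue and strain are listed in SAP 10.1 overall, by individual segment, and by fixed territory and location lists. Efficacy is exploratory, with no multiplicity adjustment, and Protocol 9.4.1 promises only descriptive summaries for cardiac structure. All of this stands and limits the point to one parameterisation of one exploratory endpoint. It does not supply a definition for controls.

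Four stronger readings are tempting, and the documents do not support them:

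- *That the whole between-arm regional comparison is invalid.* The fixed-list analyses contradict this.
- *That the segment sets certainly differ.* This needs a missed territory or remapped anatomy, and no rate is given for either.
- *That one missed territory costs 5 or 6 of 16 segments.* This ignores the exclusion of segments 2 and 3, and any such fraction applies only if territories are pooled.
- *That remapping is done with treatment known.* SAP 10.1 does not say who does it, when, or with what information. It blinds the MRI overreaders, and SAP 13.2.2 keeps core-lab staff blinded to treatment until the final 12-month analyses. The supportable statement is that assessor, timing and blinding of the remapping are unspecified. Text on the infusion procedure in Protocol 6.10.1 and near the coronary-anatomy sentence in SAP 3 is redacted, so some anatomical detail may simply be out of view.

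**Conclusion.** The point holds for the territory-level wall-motion parameter. Its stated definition cannot be computed in usual care. The obvious repair, default map for controls and infused segments for CAP-1002, makes the comparison unlike whenever a territory is missed or anatomy is remapped.

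The size is conditional. Under pooling, an affected subject loses 29-36% of the analysable segments. Under separate territories, an affected subject drops out of that territory's comparison. For an assumed 1 to 4 of 12 CAP-1002 subjects affected and a set difference of 0.25 to 1.0 SD, the shift is 0.02 to 0.33 SD and two-sided type I error is 0.050 to 0.129. The effect could therefore be negligible or noticeable. Its direction cannot be predicted from the documents. The consequence is small because the endpoint is exploratory. It deserves correcting because it is avoidable at almost no cost.

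**What to change.** In SAP 10.1:

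1. For between-arm tests of wall motion by coronary territory, apply the default LAD, LCX and RCA lists to all analysed subjects in both arms, whether or not the territory was infused.
2. Report infused-segment and anatomy-specific averages as a descriptive summary for CAP-1002 only, without a between-arm p-value.
3. Reconcile the RCA wall-thickening example with the exclusion of segments 2 and 3. State whether the exclusion covers wall thickening, and give the resulting lists.

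In SAP 2.3.2, apply rules 1 and 2 to the infusion-location grouping named for LGE and circumferential strain, so that the same gap does not reach those endpoints.

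The cost is SAP wording only: no new data, visits, readings or subjects. The fixed map may fit a subject with variant anatomy less well, but it does so by the same rule in both arms, and the descriptive summary keeps the anatomy-specific view.

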## **10.2 Mobility Parameters**

### **10.2.1 PUL Scale**

The PUL Scale consists of an entry item to define the starting functional level and 21 items subdivided into shoulder level (4 items, maximum score = 16), middle level (9 items, maximum score = 34), and distal level (8 items, maximum score = 24) dimensions. The three dimensions will be summed to derive an overall score (maximum = 74) as well as an overall score that excludes the shoulder dimensions (maximum = 58). The minimum score for all three dimensions is 0. Increasing scores over time indicate improvement. Observed values and absolute changes from baseline, overall and for each dimension separately, will be listed and summarized. A summary table will include p-values for treatment group comparisons of changes from baseline.

### **10.2.2 Spirometry**

Spirometry parameters include peak expiratory flow (PEF), forced expiratory volume in 1 second (FEV1), forced vital capacity (FVC), FEV1/FVC x 100, forced expiratory flow at 25-75% of FVC (FEF25-75%), and forced expiratory time (FET). Observed values, percent of predicted, and absolute and percent changes from baseline will be listed and summarized. A summary table will include p-values for treatment group comparisons of changes from baseline. Extreme outliers, defined as any observation outside the range [q1 – 3(q3 – q1), q3 + 3(q3 – q1)] where q1 and q3 are the 25th and 75th percentiles, respectively, over all observations for a given parameter (regardless of time point) will be excluded from summaries and analyses.

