## 6.9 Clinical Function and Quality of Life Measures

At the screening, 6 Weeks, 3 Months, 6 Months, and 12 Months (or Early Termination) study visits, the subject will be asked to complete the Performance of Upper Limb (PUL) assessment and spirometry. Both the subject and the parent/guardian will be asked to complete the Pediatric Quality of Life Inventory (PedsQL) and the PODCI Adolescent Questionnaire (PODCI).

In addition, subjects assessed by the Investigator as capable of performing the Six Minute Walk Test (6MWT) will do so at screening, 6 Weeks, 3 Months, 6 Months, and 12 Months (or, Early Termination) study visits. Subjects unable to perform the Six Minute Walk Test at screening will not be required to perform the test at any subsequent visit.

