### 3. STUDY DESIGN AND SCHEDULE OF EVENTS

This is a randomized, open-label, controlled phase 2 trial designed to evaluate the safety and tolerability and explore the efficacy of CAP-1002 administered by multi-vessel intracoronary infusion in subjects with cardiomyopathy secondary to DMD. Approximately 24, and not more than 30, subjects will be randomized 1:1 to receive CAP-1002 or usual care. Subjects randomized to receive usual care will continue to be cared for and treated on an ongoing basis in whatever manner the investigator deems most appropriate for the subject. The first 6 subjects enrolled (Group 1) will be older than 18 years of age. Enrollment of the remaining subjects (Group 2) will begin at least two weeks after the final infusion occurs in Group 1 to allow a review of Group 1 safety data through 72 hours post infusion. Subjects in Group 2 will be at least 12 years of age.

CCI

Anatomically  
one of the three coronary arteries infused must supply more than 30% of the LV myocardium.

Subjects will undergo protocol assessments through 12 months post infusion or reference date. Reviews by a Data Safety Monitoring Board (DSMB) will be done after Group 1 completes 72 hours of follow-up and throughout the trial per charter but at least semi-annually. The DSMB will review both safety and efficacy data after all subjects complete 6 months of follow-up or withdraw from the study. In addition, there will be one administrative interim efficacy analysis after Month 6 MRI measurements are available for at least 14 subjects. Subjects will be followed annually for 5 years post infusion or reference date. The Schedule of Events is shown in [Appendix A](#). A schematic of the study design is as follows:

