#### 7.5 Missing Data

- Listings will present data as reported.
- Missing or partially missing dates that are required for date-dependent definitions (e.g., treatment-emergent AEs, concomitant medications) will be assumed to be the most conservative date possible. For example, an AE with a completely missing start date will

be considered treatment-emergent; similarly, an AE that started the same month and year as IP administration but with missing start day will be considered treatment-emergent.

- Handling of missing endpoint data in summaries and analyses for each endpoint is described in Sections 8-10.

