# 10. EXPLORATORY EFFICACY ANALYSIS

Listings of efficacy parameters will be done for the ITT population. Summaries and analyses will primarily be done for the mITT population; some or all summaries and/or analyses may also be done for other analysis populations defined in [Section 6](#). In addition, “last observation” analyses will be done for certain parameters for which some subjects’ final assessments were done too late to be included in the Month 12 analysis window.

Unless otherwise noted, for the final analysis changes from baseline will be analyzed using general linear models with baseline values as covariates. Analyses of the effect of treatment group, time (baseline, Month 6, Month 12), and their interaction will be done using mixed effects linear regression, with subject as a random effect, time and treatment group as fixed effects, and baseline as a covariate. Study site may also be included as a random effect if there is evidence of correlation within study sites (per the interclass correlation coefficient from the unconditional model) and/or if doing so appreciably improves the model fit (e.g., per Akaike’s Information Criterion). Residuals will be evaluated for substantial departure from normality and independent and constant variance and appropriate remedies (e.g., data transformations, detecting and assessing the influence of outliers, alternative analytical approaches) will be attempted when necessary. An unstructured covariance will be the default covariance structure but other structures (e.g., compound symmetry) may be used to evaluate sensitivity to the choice of structure or, if necessary, to achieve convergence.

For the analysis of LV LGE rate of change since baseline compared to rate of change from historical MRI to baseline, rate of change  $RC(t_i)$  for time point  $t_i$ ,  $i = 1$  to 3 (baseline, Month 6, Month 12, respectively), will be calculated as

$$RC(t_i) = (X(t_i) - R(t_i)) / D(t_i)$$

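### The spirometry outlier rule excludes values from analysis on their size alone, so for skewed parameters it can drop valid high readings

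*SAP*

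**What the plan says.** SAP 10.2.2 covers six spirometry parameters: PEF, FEV1, FVC, the FEV1/FVC ratio, FEF25-75% and FET. For reporting it says "Observed values, percent of predicted, and absolute and percent changes from baseline will be listed and summarized".

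The exclusion rule follows: "Extreme outliers, defined as any observation outside the range" from q1 − 3(q3 − q1) to q3 + 3(q3 − q1). The quartiles are taken "over all observations for a given parameter (regardless of time point) will be excluded from summaries and analyses". Nothing splits the pool by subject, arm, age or ambulatory status, and value is the only criterion.

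Three other places bear on this:

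- SAP 7.5 says "Listings will present data as reported", so an excluded value remains visible there.
- SAP 10 deals with outliers generally by examining model residuals. Its possible remedies include transformation and "detecting and assessing the influence of outliers", to be tried when needed. It does not call for automatic exclusion.
- SAP 10.1, 10.2.1 and 10.2.3 (MRI, PUL, 6MWT) contain no comparable rule, and no reason is given for treating spirometry differently.

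**The concern.** A fence built from the pooled distribution asks whether a value is unusual among all subjects and visits. A faulty reading is one that is implausible for that subject on that day, which is a different question. Eligibility runs from age 12 into adulthood (Protocol 4.2), and the trial takes both ambulatory and non-ambulatory subjects (SAP 7.4). A subject with well-preserved function could therefore lie far from the rest with nothing wrong in his readings.

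The consequences fall on a small trial of about 12 subjects per arm (SAP 4). The analysis uses change from baseline with baseline as covariate (SAP 10), so losing a baseline value removes all of that subject's change scores for the parameter. The mITT population is defined separately for each parameter by having a post-baseline observation (SAP 6), and the SAP does not say whether an excluded value still counts as one. Because the scale of the fence is unstated, two analysts following the text could exclude different values. The quartiles also move as data accrue, so the excluded set can differ between the Month 6 analysis, whose top-line results are to be made public (SAP 13.2.2), and the final analysis.

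**Working it through.** The documents give no expected number of exclusions and no spirometry mean, SD or skewness, so there is no plan figure to reproduce. The check asks how often the rule excludes a value when **every value is valid**.

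**Inputs from the documents.** SAP 3: "Approximately 24, and not more than 30, subjects will be randomized 1:1 to receive CAP-1002 or usual care". Protocol 6.9 schedules spirometry "At the screening, 6 Weeks, 3 Months, 6 Months, and 12 Months (or Early Termination) study visits", which is five visits. The pool per parameter is 24 × 5 = 120 to 30 × 5 = 150 values.

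**Inputs assumed.** The shape of the distribution (normal, or lognormal with log-scale SD s), and a within-subject correlation of 0.9.

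**Normal data.** q3 lies 0.6745 SD above the mean and the interquartile range is 1.349 SD. The fence is at 0.6745 + 3 × 1.349 = 4.72 SD. The two-sided tail is 2.3 × 10⁻⁶, so the expected number of exclusions is 120 × 2.3 × 10⁻⁶ ≈ 0.0003 per parameter, or about 0.002 over six parameters. With sample quartiles and five correlated visits per subject, simulation gives about 0.5% to 1% of trials losing any value of a parameter.

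**Right-skewed data.** With the median set to 1, q1 = exp(−0.6745s), q3 = exp(0.6745s), the upper fence is U = q3 + 3(q3 − q1), and the tail probability is 1 − Φ(ln U / s). For s = 0.5: q1 = 0.714, q3 = 1.401, U = 3.463, ln U / s = 2.484, tail 0.65%, and 120 × 0.0065 = 0.78 expected values.

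The last two columns below are from simulation of 24 subjects × 5 visits, with the fence as SAP 10.2.2 defines it, applied to raw values.

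| s | Upper fence (× median) | Tail | Expected of 120 | Trials losing ≥1 valid value | Trials where some subject loses exactly one of baseline and Month 12 |
|---|---|---|---|---|---|
| 0.3 | 2.45 | 0.14% | 0.17 | 12% | 5% |
| 0.5 | 3.46 | 0.65% | 0.78 | 33% | 16% |
| 0.7 | 4.54 | 1.5% | 1.8 | 57% | 27% |
| 0.9 | 5.71 | 2.7% | 3.2 | 75% | 38% |

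A separate calculation indexed by coefficient of variation agrees: 11% to 13% of trials at CV 0.3, 30% to 35% at 0.5, 48% to 55% at 0.7 and 69% to 77% at 1.0, for 24 to 30 subjects.

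**Direction.** The lower fence is negative when q1 < 3(q3 − q1), that is, when q3/q1 > 4/3. At s = 0.3 the ratio is already exp(2 × 0.6745 × 0.3) = 1.50. Spirometry values are positive, so a negative lower fence can exclude nothing. No low value was excluded in any skewed run.

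**Effect on the comparison** (simple arm difference in Month 12 change, not the SAP's full model):

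- With no treatment effect, the difference stayed unbiased (mean within 0.001 of zero). Its spread, without and with the fence, was 0.0595 and 0.0589 at s = 0.3, and 0.116 and 0.110 at s = 0.5. It fell materially only at 0.7 and 0.9.
- With an assumed 20% multiplicative benefit, the fence shrank the difference by about 1%, 4%, 11% and 18% across the four values of s.

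**Interim against final.** The set of values through Month 6 that is excluded differed between the two analyses in 4%, 8%, 13% and 15% of simulated trials.

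**The case against.** The rule has real merits. It is prespecified, objective and blind to arm, the fence is wide, and it cites a standard text on exploratory data analysis. Pooling different subjects tends to widen the interquartile range and so makes exclusion rarer. The approach in SAP 10 is discretionary, and outlier decisions made after seeing data in an open-label trial carry their own risk of bias. All of this stands. It is a reason to keep a prespecified rule, but not to let that rule exclude values nobody has checked.

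It can also be said that data are checked anyway: Protocol 11.10 describes queries to sites, and SAP 13.3 requires quality control and query resolution before the final analysis. Neither is tied to the fence. A value that passes those checks is still excluded.

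The larger percentages rest on skewness that no document supports, and no parameter is identified as that skewed. This stands, and it makes the finding conditional. The shifting fence is a small matter as well, since SAP 13.2.2 gives the Month 6 analysis no role in trial design or conduct.

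Three stronger readings are tempting and are not supported:

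- A reader might infer that values are deleted from the record. They are not; they remain in the listings.
- A reader might infer that real large declines are removed. On raw skewed values the exclusions are all high. A decline would be lost only if the subject's high baseline were excluded, or possibly if the fence were applied to change scores, which the SAP leaves open and which was not simulated.
- A reader might infer that the treatment comparison is certainly biased. Under no effect it was not, and under an assumed effect the shrinkage was small unless skewness was high.

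**Conclusion.** The point holds as a conditional risk of minor severity. As written, SAP 10.2.2 excludes spirometry values on distribution alone, without verification, without a retained-value analysis and without naming the scale.

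For near-normal parameters this hardly matters. For right-skewed parameters, the chance per parameter of losing at least one valid value runs from 12% at a log-scale SD of 0.3 to 75% at 0.9. Attenuation of a real difference becomes noticeable only towards the upper end (about 11% at 0.7 and 18% at 0.9, for a 20% benefit). These figures assume lognormal values, within-subject correlation of 0.9, 24 subjects with complete visits, and the fence applied to raw values. Spirometry is one of several exploratory efficacy measures in a trial whose primary objective is safety, so no main conclusion turns on it.

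**What to change.** Amend SAP 10.2.2 as follows:

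1. Use the fence only to trigger a data query against source.
2. Exclude a value only for a documented technical failure, decided blind to treatment arm and before database lock.
3. Keep every confirmed value in the main summaries and analyses.
4. State the scale on which the fence is computed (raw value, percent predicted or change).
5. Report the fence-excluded analysis as a sensitivity analysis, with the number of flagged values by arm and visit.

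The cost is a few lines of SAP text, some queries and one additional run. The downside is that a genuine outlier kept in the main analysis may widen a standard error; the residual checks and transformations already allowed in SAP 10 are available for that. This is a cheap improvement.
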